Before treatment, there will be a 4 week observation-only period, and another one 8 weeks post-treatment, so that the total study period will be 6 months.

We aim for 20 patients to be included in this study.

see more detailed graphics in the next section

In terms of ancillary, laboratory-based studies, we intend to draw blood before treatment and at the 45-, 75-, 105- and 135-day of treatment time-points. We will measure cytokine/chemokine/lipid pain- and inflammation markers in patients' serum, also determine microRNA in their serum, and genomic DNA polymorphisms, the latter only at baseline. Please see next section for more detail.

To establish safety of the anti-CGRP treatment in this patient cohort, blood draw at baseline and at the 45-, 75-, 105- and 135-days of treatment time-points will also include routine systemic sentinel/surveillance markers, namely comprehensive metabolic panel and complete blood count with differential, and complete urinalysis. No more than 45 ml of blood will be collected at any given visit.

In terms of additional safety parameters, we propose an open, patient-kept side-effect log, plus home-based recordings of blood pressure, heart rate and weight at a frequency of 2x/week.

We will set up a data and safety monitoring board for proper management and oversight of data handling and patient safety-related issue; see next section.

[figure not shown]
We expect to observe effective treatment, at least in a significant subgroup of patients. Effectiveness of treatment, also magnitude of any observed therapeutic effect will be correlated with the pain/inflammation proteinaceous, lipid and RNA-based biomarkers in patients' serum, also with any polymorphisms in the patients' genomic DNA.

We also expect galcanezumab treatment to show another record of safe treatment, our expectation sculpted by analysis of in-depth data from treatment of migraineurs. Yet we will remain vigilant and implement the proposed safety sentinel measures in order not to miss adverse effects. This appears prudent because trigeminal or glossopharyngeal nerve pain plus small-fiber neuropathy is a different underlying disorder than migraine, likely representing a higher prevalence in peri-menopausal female patients. We also believe it is likely that level of chronic pain suffering-associated stress will be higher in our study population than in migraineurs.

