Each page is intended for 1 day. For each day, they will record a summary pain rating on a visual analog scale (VAS) from 0-10. Also for each day, they will document all medications taken, listing analgesic medication first, both prescription as well as over-the-counter. On another 0-10 VAS they will rate their subjective level of how energetic they felt. They will record length of sleep, night-time and daytime.

Patients will also be wearing wearable activity monitors. In case they already have such a device, it will be used (e.g iWatch, fitbit). In case they do not have one, they will be provided with such a device, a Huawei Terra-B19 Band 3 Pro. Instructions for use will be provided.

After final data acquisition by the RMT, the Huawei device will be left to the patient for their own future use.

The d180 page of the subjective rating protocol will contain the question "*Do you want to continue using Emgality (galcanezumab) for s.c. injection?*"

Importantly, handling and acquisition of these data will not record any HIPAA-pertinent PHI because the activity monitor will not record or store any of these. The 200-page booklet will be tagged with a unique ID number in front, back and on the side of the pages, being mindful not to include any PHI.

For 2x/week measurement of blood pressure, heart rate and body weight, patients will be supplied with the following devices so that these metrics can be acquired in their domestic environment:

home scale for body-weight

blood pressure and heart rate monitoring device

5) Patient Training and Instructions

At the initial visit, patients will receive detailed instructions how to fill out the subjective rating booklet, how to self-inject, and how to wear, use and handle the activity monitors, in case they will be provided with one, or how to make sure that their own activity monitor will record activity and sleep as intended.

Training how to self-inject Emgality will be provided by the study staff. Patients will also be provided with written instructions.

It will be verified that they understand the need to record and document blood pressure, heart rate and body weight 2x/week, to be documented on their daily log page.

6) Research Management Team (RMT)

The Research Management Team will consist of Principal Investigator, Sub-Investigators, Regulatory/Data Coordinator and Research Coordinator/Research Nurse

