Study site personnel must alert the Duke IRB of any SAE within 24 hours of PI or any other member of the clinical team becoming aware of the event.

If alerts are issued via telephone, they are to be immediately followed with official notification on study-specific SAE forms. This 24-hour notification requirement refers to the initial SAE information and all follow-up SAE information.

Pregnancy does not meet the definition of an AE. However, to fulfill regulatory requirements any pregnancy should be reported following the SAE process to collect data on the outcome for both mother and fetus.

Investigators are not obligated to actively seek AEs or SAEs in subjects once they have completed the 90-day treatment period. However, if the investigator learns of any SAE, including a death, during the 60 day observational period, the PI must promptly notify the Duke IRB. This will also apply to an SAE after finishing the study if the PI considers the event reasonably possibly related to treatment with galcanezumab or study participation.

Suspected unexpected serious adverse reactions (SUSARs) are serious events that the investigator identifies as related to galcanezumab or procedure. United States 21 CFR 312.32 and European Union Clinical Trial Directive 2001/20/EC and the associated detailed guidances or national regulatory requirements in participating countries require the reporting of SUSARs. The Duke IRB has procedures that will be followed for the identification, recording and expedited reporting of SUSARs that are consistent with

global regulations and the associated detailed guidances.

Enrolled patients will be instructed to contact the PI and his study team as soon as possible if the patient has a complaint or problem with galcanezumab so that the situation can be assessed.

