For the rationale to have the above specific inclusion criteria, see "Abstract" on p3, and "Purpose" on p4. Very briefly, (i) access to the respective patient population appears not limited, (ii) neurogenic inflammation is strongly considered to function pro-algesically in trigeminal nerve pain (and by inference in glossopharyngeal nerve pain) **and** in small fiber neuropathy-associated pain, (iii) trigeminal or glossopharyngeal nerve pain associated with small fiber neuropathy/ fibromyalgia appears to be a hitherto unrecognized particular variant of painful cranial nerve disorder. Re point (i), this could be related to the development that the PI's clinics have become US national go-to centers for painful cranial nerve disorders. Especially re argument (iii), the phase Ib treatment study as proposed here will help us to define better this new pain disorder, which we strongly feel deserves separate and explicit recognition, also in terms of treatment response.

Age-wise, the protocol applies to patients between 18 and 80 years old.

Patients that have a history of allergy or allergy-like incompatibility with a biologic that contains a human or humanized monoclonal antibody will be excluded.

Likewise female patients of child-bearing age who are or want to become pregnant will be excluded. In case such a patient intends to participate, then she has to commit to a pregnancy prevention regimen that is based on hormonal contraceptive or intra-uterine device. This is stated explicitly in the Informed Consent Form.

These exclusion/ inclusion-relevant points will be ascertained and discussed explicitly during the initial visit. Agreement between patient seeking enrollment and investigator will be documented in the patient's electronic health record and in the ICF. As for the pregnancy issue, in female patients of child-bearing age, a pregnancy test will be administered at first visit.

9) Standard-of-care vs activities to be carried by the protocol

All activities related to the study as listed under **1) Timeline** will be carried by the protocol. In case safety-related laboratory parameters (comprehensive metabolic panel, complete blood count and urine-analysis) will be needed under a standard-of-care approach, then this will be followed and resulting data will be perused for this study. In all other cases and circumstances, the clinical activities will be carried by this protocol.

10) Recruitment plan

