Patients will be recruited via the PI's clinics at Duke University, the Duke Clinics that typically refer to her attention and outside clinics and providers that refer to her as well, and DEDUCE database. In case of slow recruitment patient self-help and patient advocacy associations in the facial pain arena will be informed of the ongoing study to assist with recruitment. These organizations (Facial Pain Research Foundations, Facial Pain Association) are well-known to the PI.

11) Brief Statistical Analysis Plan

Only patients who complete the study will be included in the statistical analysis.

Response to treatment will be assessed by comparing pain metrics during the 90-day treatment period vs averaged 30 day "run-in". Outcome variables will consist of selected readout parameters of "pain metrics", namely pain subjective rating on VAS (0-10) and medication co-use. Additional outcome variables include circadian rhythm-associated metrics. A daily readout for each variable will be entered into their log by each patient, or by automatic activity reads from their motion tracking device. In similar manner, we will compare pain metrics during the 90-day treatment period vs 60-day post-treatment observation.

We intend to conduct the study with an n=20 patients to successfully complete the study. This selected number appears the most feasible and practicable number. We are confident that with an n=20 we will be in a position to do justice to the objective of initial assessment of the safety of galcanezumab in the condition under study, trigeminal or glossopharyngeal pain in the context of painful small fiber neuropathy/fibromyalgia.

Following completion of the study, we will have estimates of effect sizes and corresponding 95% confidence intervals providing information on the precision of the statistical estimates of treatment effect. Power analysis will be performed based on these estimates and will provide us with guidance for sample sizes of follow-up studies that aim for demonstrating effectiveness.

The statistical analysis will be based on a linear mixed model for repeated measures. The

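### Section 8 sets the pregnancy test at the first visit, by inference 28 to 30 days or more before the first 240 mg dose, and no readable text states a re-test

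*Combined protocol and SAP*

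**What the plan says.** Pregnancy appears under Exclusion Criteria in the overview and again in section 8, which also excludes women planning a pregnancy and requires hormonal or intra-uterine contraception from women of child-bearing age who take part. Section 8 fixes when eligibility is checked: "These exclusion/ inclusion-relevant points will be ascertained and discussed explicitly during the initial visit". It then gives the timing of the test: "As for the pregnancy issue, in female patients of child-bearing age, a pregnancy test will be administered at first visit".

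The sequence before dosing comes from three other places.

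- Study Design / Overview: "Before treatment, there will be a 4 week observation-only period". The same section gives the regimen as 240 mg, then 120 mg and 120 mg, at 4-week intervals.
- Section 5: "At the initial visit, patients will receive detailed instructions how to fill out the subjective rating booklet, how to self-inject".
- Section 11: the response analysis rests on "comparing pain metrics during the 90-day treatment period vs averaged 30 day" run-in values, and on the source of the data it says "A daily readout for each variable will be entered into their log by each patient".

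The safety laboratory tests listed in the overview are a metabolic panel, a blood count and urinalysis; a pregnancy test is not among them. Section 7 deals with pregnancy as something to report: "any pregnancy should be reported following the SAE process to collect data on the outcome for both mother and fetus".

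**The concern.** An exclusion that protects against drug exposure should be verified close to the first exposure. As section 8 reads, it is verified at enrolment, and a drug-free month follows before the first and largest dose. A woman who tests negative at the first visit because conception is too recent, or who conceives during the run-in, could reach the 240 mg injection without knowing that she is pregnant. Reporting under section 7 would then come after exposure.

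Safety is the trial's primary criterion, so a check that the plan clearly intends should sit where it does its work. What is at stake is one avoidable exposure in a small trial. No estimate, comparison or error rate depends on it.

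**Working it through.** **Step 1. Check the timeline.** Section 11 gives a 30-day run-in, 90 days of treatment and 60 days of follow-up: 30 + 90 + 60 = 180 days. This matches the day-180 booklet page in section 4 and the 6-month total in the overview. The overview's own weeks give 4 + 12 + 8 = 24 weeks = 168 days, about 5.5 months, which agrees only loosely. The day-180 page therefore fits a booklet counted from the first day of the run-in.

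**Step 2. Place the first visit.** No section dates the first visit against the first injection, so the gap is inferred:

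- Run-in pain and medication values come from the patient's daily log (section 11).
- Patients are taught to complete the booklet at the initial visit (section 5).
- The initial visit is therefore no later than day 1 of the run-in.

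This takes the first visit and the initial visit of section 8 to be the same visit.

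**Step 3. Age of the test at first dose.** With 4 weeks: 4 × 7 = 28 days. With the section 11 wording: 30 days. Both are minimum values, because the visit may precede day 1 of the run-in.

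**Step 4. Look for another test.** In the readable text, pregnancy appears as an exclusion, in the section 8 contraception and testing rules, and in the section 7 reporting rule. None states a second test.

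**Step 5. Illustrative size.** The documents give neither the number of women of child-bearing potential nor a conception risk, so both are assumed: n = 3 to 10 of the 20 patients, and a monthly risk p on the required contraception. Over about one month, the chance of at least one pregnancy at first dose is 1 − (1 − p)^n.

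| Assumed monthly p | Annual equivalent, 1 − (1 − p)^12 | n = 3 | n = 5 | n = 10 |
|---|---|---|---|---|
| 0.05% | 0.60% | 0.15% | 0.25% | 0.50% |
| 0.1% (base) | 1.19% | 0.30% | 0.50% | 1.00% |
| 0.2% | 2.37% | 0.60% | 1.00% | 1.98% |

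Given the inputs, these figures are upper bounds on what a re-test could prevent. They count every conception, including any that the patient recognises before dosing and any too recent for a urine test to detect.

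**The case against.** The strongest objection is that the argument rests on an absence in incomplete text. Section 9 refers to "All activities related to the study as listed under" the timeline in section 1, and that schedule could not be read. A pre-dose test would most naturally be listed there. A reader might infer that the trial has no pre-dose test; the documents do not support that. What stands is narrower: section 8 is where the plan sets out pregnancy testing, and it places the test at the first visit.

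Second, the plan already controls the risk in layers: it excludes women who are pregnant or planning pregnancy, requires contraception, records the agreement in the health record and consent form, and tests once. This makes an exposed pregnancy unlikely, but it does not verify the exclusion when the drug is first given.

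Third, a reader might infer that anyone who conceives during the run-in would be dosed. That goes too far. A pregnancy recognised in that month already falls under the exclusion, so only an unrecognised one can slip through.

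Fourth, the probabilities are built on assumed inputs. The overview expects the condition to be more common in peri-menopausal women, which makes n = 10 look generous. This is a fair criticism, and the figures should be read only as an order of magnitude.

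Last, the same 4-week interval recurs before doses 2 and 3. If contraception is enough there, it might be thought enough during the run-in. But first exposure is the point that an entry exclusion guards, and leaving later doses untested does not make a check before that point a mere preference.

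**Conclusion.** The point holds as a minor safety refinement. Under section 8 as written, the pregnancy exclusion is tested about 28 to 30 days or more before first exposure, and an unrecognised pregnancy arising around the first visit or during the run-in would not be detected before the 240 mg dose.

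The gap rests on two inferences: that the first visit is the one at which booklet training takes place, and that this training precedes the run-in. The probability is low. The base case is 0.3% to 1.0% for the whole trial and the widest range shown is 0.15% to 2.0%; the preventable part is smaller, and every input to those figures is assumed. Efficacy analyses and sample size are untouched. It would be wrong to read this as a serious safety failure, or as proof that the trial never re-tests.

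**What to change.** Keep the first-visit test and add one sentence to section 8:

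> Women of child-bearing age repeat a urine pregnancy test at the end of the run-in, immediately before the first injection (at home, with the result reported to the site, if self-injecting); a patient with a positive result does not start galcanezumab.

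The cost is one test strip per woman of child-bearing age (3 to 10 strips under the assumption above), brief staff time to log the result, and a short edit to the consent form. A urine test can miss a very recent conception, so this shortens the unverified window without closing it.

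Check the schedule of activities first. If it already shows a test before the first dose, nothing operational changes and section 8 only needs to say the same.

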Treatment with a CGRP-neutralizing antibody, galcanezumab in this specific patient group, being seen in the PI's clinics on a regular basis, is rooted in the rationale of unmistakable presence of clinical signs of neurogenic inflammation in the painful territory, such as episodic swelling combined with redness/hyperemia, also relief by external cold application which typically patients with trigeminal or glossopharyngeal nerve pain abhor.

Primary Outcome Measures

Primary criterion is to establish an excellent safety profile that recapitulates the favorable data recorded in migraineurs. The primary pain-related objective is reduction of pain and reduced use of rescue and other anti-pain medication.

Inclusion Criteria

- G50.1 diagnosis (can encompass an add-on G50.0 and other headache G43.... codes), or G52.1 diagnosis code (with explicit mentioning of pain of glossopharyngeal origin) **AND** small fiber neuropathy diagnostic codes G63.3, G60.8, G62.8 (can encompass fibromyalgia diagnostic code M79.7)
- 18-80 years old
- not allergic to galcanezumab and other hu mAb biologics

Exclusion Criteria

- allergic to galcanezumab and other hu mAb biologics
- pregnancy

Study Design / Overview

We propose to treat patients open label for 12 weeks, with galcanezumab, supplied by Eli Lilly, as add-on to all other therapeutic measures. We propose to use a 240mg/120mg/120mg regime, with subcutaneous (self-)injections every 4 weeks.

To reflect pain experienced by patients, the primary read-out is pain level on a 0-10 visual analog scale. We will be prompting patients to record a daily summary read at the end of each day.

[figure not shown]
The second criterion is reduction of intake of anti-pain medication (rescue PRN or regular) which the patients will record.

Chronic pain, especially fibromyalgia pain combined with trigeminal or glossopharyngeal nerve pain, is a potent disruptor of circadian rhythm. We strongly believe that this is an important and hitherto under-appreciated contributor to individual disease burden. Therefore, the third criterion is assessment of circadian rhythm function. We will assess this by having the patient rate subjectively how energetic they feel during awake day-time. Wearable activity monitors will be used to address how many hours patients sleep per

24h period, with detailed focus on total duration of sleep/rest and duration of night-time sleep only.

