time course of pain metrics reported during the treatment period will be compared with metrics during the run-in baseline. The covariance matrix describing the nature of correlations between repeated measures will be selected based on Akaike information criterion and Bayesian information criterion, as guided by our statistics software, SAS/STAT15.1. p-values <0.05 will be considered statistically significant. Effects of treatments will be investigated with the introduction of treatment as a binary covariate (we will evaluate the effects of pre- and post-treatment in two different models).

Patients' anti-pain treatment response will be correlated with blood markers for pain, inflammation and miRNA, and also for genomic markers. This approach will be pursued in order to identify candidate biomarkers that pre-dispose patients to experience an effective or non-effective treatment response. In case of recording any particular safety-related parameters, correlation of these markers to safety metrics will also be conducted. Association between molecular biomarkers and pain- and activity-related metrics will be evaluated (i) at each time point separately using a linear regression model; (ii) by modeling the association across all time points and including time covariate in the linear regression model. The ensemble of these approaches will help determine the periods when pain or activity-related metrics and molecular markers co-evolve and become highly correlated.

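### The completer-only rule discards pain diaries that the planned mixed model could use, and it leaves open which patients count for safety

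*Combined protocol and SAP*

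**What the plan says.** Section 11 opens with the population rule: "Only patients who complete the study will be included in the statistical analysis". It gives no exception and no definition of completion.

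The main pain analysis is then set out: "Response to treatment will be assessed by comparing pain metrics during the 90-day treatment period", against the average of a 30-day run-in. A second comparison follows: "In similar manner, we will compare pain metrics during the 90-day treatment period vs 60-day post-treatment observation". The two are fitted as separate models. The method is given as: "The statistical analysis will be based on a linear mixed model for repeated measures". The effect sizes and 95% confidence intervals have a further use: "Power analysis will be performed based on these estimates and will provide us with guidance for sample sizes of follow-up studies".

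On sample size, Section 11 states: "We intend to conduct the study with an n=20 patients to successfully complete the study". The Abstract instead gives 20 as the enrolment target, and the Study Design / Overview gives it as the number included.

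On safety, Primary Outcome Measures states: "Primary criterion is to establish an excellent safety profile that recapitulates the favorable data recorded in migraineurs". The outcome variables listed in Section 11 are pain rating, medication co-use and circadian metrics. Its one safety analysis is conditional: "In case of recording any particular safety-related parameters, correlation of these markers to safety metrics will also be conducted". It names no AE summary and no safety analysis set.

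**The concern.** The rule makes entry to every comparison depend on reaching the end of the study, whatever data that comparison needs. The run-in versus treatment comparison uses the first 120 diary days. The last 60 serve only the second model. A repeated-measures mixed model is commonly chosen because it accepts unequal numbers of observations per patient, so a completer restriction gives up that advantage.

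Two things are at stake for pain. One is precision, in a study of about 20 patients. The other is direction: if patients with poor relief leave more often, those who remain look better than the treated group as a whole. There is no control arm to offset this, and the estimate is to be used to size later trials.

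Safety is a secondary point. It is the study's primary criterion, yet Section 11 does not say who is counted or how AEs are summarised, and its only population rule is one that removes early leavers.

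**Working it through.** **1. What completion means.** The text does not define it.
- Study Design / Overview counts the post-treatment observation in the study period and gives a total of 6 months. In weeks, 4 + 12 + 8 = 24 weeks = 168 days. In Section 11's days, 30 + 90 + 60 = 180.
- Section 4 places a question on the day-180 diary page.
- Section 7 treats completing the 90-day treatment period, the 60-day observation and the time after the study as separate stages.

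These favour the full period. Section 7 also speaks of stopping galcanezumab before completing the study, which is looser. Nothing says whether a patient who stops injections but stays under observation is a completer.

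**2. What the main comparison needs.** 30 + 90 = 120 of 180 days (67%). On the full-period reading, a patient who leaves on day 130 has all 120 and is still dropped. On the 90-day reading that case disappears, but patients who leave during treatment are dropped on both.

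**3. Precision.** The documents give no SD or dropout rate. Assume an SD of 1.5 VAS points for the patient-level change. Half-width = t(0.975, n−1) × 1.5/√n.

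| n analysed | Half-width | SE |
|---|---|---|
| 14 | 0.87 | 0.40 |
| 16 | 0.80 | 0.38 |
| 18 | 0.75 | 0.35 |
| 20 | 0.70 | 0.34 |
| 22 | 0.67 | 0.32 |
| 24 | 0.63 | 0.31 |
| 26 | 0.61 | 0.29 |

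- If 20 are enrolled and 2, 4 or 6 leave, read upward from 20: 0.70 becomes 0.75, 0.80 or 0.87.
- If 20 complete and 2, 4 or 6 others leave, read downward: including them could narrow 0.70 to 0.67, 0.63 or 0.61. This is a best case, because partial diaries carry less information than full ones.

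**4. Bias of the completer mean.** Assume 20 treated, true mean change 0, SD 1.5, and m leavers drawn with probability weight exp(k × change), where a positive change is worse pain. Because the overall mean is 0, bias = −m/(20−m) × (leavers' mean change). Example: m = 4, k = 0.5, leavers' mean +0.90 gives −4/16 × 0.90 = −0.225; simulation (100,000 trials) gives −0.223.

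| Link | Leavers worse by | Shift toward benefit, 2 / 4 / 6 leave |
|---|---|---|
| none (k=0) | 0 | 0 / 0 / 0 |
| weak (0.25) | 0.51 / 0.48 / 0.44 | 0.06 / 0.12 / 0.19 |
| medium (0.5) | 0.99 / 0.90 / 0.81 | 0.11 / 0.22 / 0.35 |
| strong (1) | 1.67 / 1.44 / 1.25 | 0.19 / 0.36 / 0.53 |

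**5. What using all diary days achieves.** For patients who leave in follow-up, the run-in versus treatment comparison has no missing data and so no bias from their leaving. For patients who leave during treatment, assume weekly means, 4 run-in and 13 treatment weeks, leaving after 2–9 treatment weeks, between-patient SD 1.5, weekly residual SD 0.75 or 1.5, k from 0.25 to 1, 2–6 leavers, and a binary treatment covariate.

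| Change visible before leaving | Remaining bias, random intercept | With a random treatment effect added |
|---|---|---|
| all | 0.02–0.13 | 0.00–0.04 |
| half | 0.03–0.27 | 0.03–0.21 |
| none | 0.05–0.41 | 0.05–0.39 |

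Completer-only analysis in the same runs: 0.05–0.54.

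**6. Safety illustration.** Suppose 2 patients leave for an AE.
- If 20 are treated: 2/20 = 10% (exact 95% CI 1.2–31.7%). Completers alone would show 0/18 (upper limit 18.5%).
- If 20 complete: 2/22 = 9.1% (1.1–29.2%). Completers alone would show 0/20 (upper limit 16.8%).

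Neither table is planned. The figures show what an unstated population leaves open.

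**The case against.** **Completion may mean the 90-day treatment.** The schedule graphics are not shown, and a completion point could be marked there. If so, the case of full 120-day diaries falls away. Exclusion of patients who leave during treatment stands.

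**The rule may not reach safety.** Its sentence does not mention safety, and Section 11 uses the same term for the mixed model alone. This is a fair reading. A reader might infer that the plan removes AEs of withdrawn patients from its safety results. The documents do not support that: no AE rate is planned, so none loses leavers. AEs are recorded from consent, and those that lead to stopping are followed (Section 7). The DSMB reviews cumulative data (Section 3). What remains is an omission: the population and summary for the primary criterion are not stated.

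**The bias is hypothetical.** Correct. A reader might infer that the pain estimate will be biased toward benefit. The documents give no dropout rate or reasons, and with no link the bias is zero. Most of the assumed cases fall at or below one SE of the completer mean (0.35–0.40). The simulated model is also simpler than the plan, which has daily readings and a covariance structure chosen by AIC and BIC.

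**It is a small open-label pilot with a brief plan.** True, and any dropout bias sits on a change that is already uncontrolled. But each lost patient costs more in a small study, and the estimate has a stated later use.

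**Conclusion.** The concern holds in this form. The completer-only rule is unnecessary for the planned model and discards usable diaries. On the better-supported but unstated full-period reading, these include diaries complete for the main comparison.

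The precision cost does not depend on why patients leave. At an assumed SD of 1.5 it is 0.04 to 0.16 points of half-width for 2 to 6 leavers if 20 are enrolled (0.746 − 0.702 to 0.866 − 0.702). If 20 complete, it is at most 0.04 to 0.10 (0.702 − 0.665 to 0.702 − 0.606). The shift toward benefit, 0.06 to 0.53 points, arises only if dropout tracks poor relief, and its size rests wholly on assumed inputs.

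For safety the finding is a gap in specification: the rule's reach is unclear and no analysis set is named. Safety data are collected for all consented patients.

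**What to change.** - **Pain, medication and circadian outcomes.** Replace the sentence so that these use all treated patients with run-in data and every available diary day in the planned mixed model. This reduces the bias from selective dropout but does not remove it.
- **Completers.** Keep them as a sensitivity analysis. Define completion, and say whether a patient who stops injections but stays under observation qualifies.
- **Safety.** State that the completer rule does not apply. In all patients with at least one injection, summarise AEs (incidence with exact 95% CI), laboratory, urinalysis and vital-sign data, including weight, and give withdrawals by reason. Show events from the 60-day observation separately, because Section 7 ends active AE seeking with the treatment period. State the laboratory window too: the last draw is at day 135, after treatment whether days run from the first injection or from the start of run-in.
- **Sample size.** State whether n=20 means enrolled or completing.

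The cost is SAP wording, plus retrieval of partial booklets and device data from patients who withdraw, which the documents do not describe. No patients are added. The AE and pain figures may look less favourable.
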